### **Study schedule:**

The principle investigator or study coordinator will be the initial contact. Potential subjects will be approved for screening through a brief interview and intraoral examination.

- **Screening appointment:** A screening appointment will be scheduled and potential subjects will be approved after a thorough interview and intraoral and x-ray examinations. Each subject will be provided with a written consent form to read and attest with his or her signature. Patients will be assured of the privacy of their data and will receive a 3 digit number ID. All data collected will be saved in password protected computer in the principal investigator office, room 531A (key access only). The screening process will include medical and dental history, demographics, current/concomitant medication, oral soft and hard tissue examination, and a review of all inclusion and exclusion criteria (attachment # 5 and 6). Pregnancy test will be provided to childbearing women subjects at screening appointment to rule out pregnancy (to meet inclusion/exclusion criteria). The pregnancy test to be provided is First Response Pregnancy Test Stick (Church & Dwight Co. Inc).
- Subjects who are found eligible through the screening process will be evaluated preoperatively through a periapical and bitewing radiographs (**Figure 1**). The penetration of the lesion will be assessed in the bitewing radiograph according to the inclusion criteria. To obtain period-identical x-rays, a specific film holder (Super-bite; Kerr) Rinn XCP film holder will be used. An acrylic resin (Duralay) pattern will be fabricated for each subject on the biteblock of the film holder to be able to reposition it when taking follow up radiographs. Also baseline pain assessment will be recorded via visual analogue scale (VAS); and pulp vitality assessment, using palpation, cold, percussion, and EPT tests, will be completed. Data will be collected in a form (attachments #7) and inputted into a secure, web-based Research Electronic Data Capture (REDCap) application.
- **Clinical intervention:** As for any dental appointment for caries removal, the patient's medical history will be reviewed, vital signs will be taken, and standard procedures for caries removal and restoration will be done. These include local anesthesia and rubber

dam isolation. The caries will be accessed aseptically with conventional burs and high speed hand piece instruments.

- These preliminary procedures will be the same for direct and indirect pulp capping therapies. Three restorative protocols will be investigated in indirect pulp capping cases (see below protocols A, B, C) and two restorative protocols will be investigated for direct pulp capping (see below: protocol A and B). The protocol C is not indicated for direct pulp capping.
- Treatment protocols will be randomized and the subjects will be treated as follow:
  - o Protocol A: Use of an intermediate layer of TheraCal LC between cavity floor and adhesive system/resin composite. Theracal LC will be applied directly to the cavity floor in increments of 1mm thickness. The layer will be light cured for 20 seconds, as recommended by the manufacturer's instructions.
  - o Protocol B: Use of an intermediate layer of Dycal between cavity floor and adhesive systems/resin composite. Base and accelerator pastes will be equally dispensed, mixed, and immediately applied at the deepest portion of the preparation following manufacturers instructions. A thin layer of conventional glass ionomer (Vitrebond – 3M ESPE) will be applied over the Dycal and light cured for 30s as recommended by the manufacturer.
  - o Protocol C: No placement of an intermediate material between cavity floor and adhesive system/resin composite.
- Following the above procedure, every tooth, regardless of the above protocol, will be restored following the traditional steps for resin composite restorations. The remaining enamel of the cavity wall will be selectively etched with Bisco's Select HV Etch. The acid will be rinsed thoroughly and excess water will be removed with high suction and/ or cotton pellets leaving the preparation visibly moist. Two separate coats of adhesive (All-Bond Universal) will be scrubbed into the preparation with a microbrush for 10-15 seconds per coat. The excess solvent will be evaporated and the adhesive will be light cured for 20 seconds.
- Resin composite (Aelite LS Posterior, Bisco) will be used incrementally (3-5 increments) to fill in the remaining cavity and each increment will be cured for 40 seconds. Patient's occlusion will be checked and adjusted if needed. Once patient is satisfied with the restoration, a bitewing radiograph will be taken as a baseline post-treatment documentation of the restoration and remaining dentin thickness (layer of dentin between the restoration and the pulp). Once the restoration is complete and the patient is satisfied, a bitewing radiograph will be taken. All subjects will be given post-operative instructions (attachment #5) and the following appointment will be scheduled. Post-operative instruction will be given to the patient.
- **Phone call follow up: 24h and 1 week:** Subject will be reached ~~interviewed~~ by phone (script) 24 hours and one week after the intervention to remind them to complete the pain assessment form. Electronic (via REDCap) or printed forms (with pre-stamped envelopes) will be provided to the subjects. Survey will ask the patient to assess their pain using the visual analog scale (attachment #8).
- **Follow up appointments at 3 months, 6 months, and 12 months after procedure:** At 3 months, only a clinical examination will be completed. At 6 and 12 months, periapical and bitewing radiographic evaluation will be performed for research purposes. Pulp vitality and

pain will be assessed at each follow up appointment using the respective forms. All gathered data will be inputted into the REDCap application. Pregnancy test will also be provided to childbearing women subjects at 6 months follow up (where x-rays will be taken for research purposes) and 12 month follow-up (where x-rays will be taken for research purposes). If pregnancy is detected during the trial, the subject will be immediately removed from the study.

All subjects will attend the College of Dentistry for a total of 5 times of approximately 1-2 hours each in a one year period for an approximate 6 hours. There will be a screening appointment for data collection and review inclusion and exclusion criteria for subject selection. The next appointment will be the intervention, where the patient's decayed tooth selected for the study, will be treated and restored. Treatment will be randomly assigned to each subject. The 3, 6 and 12 months appointments will be follow up appointments for data collection. (See above for further details of each appointment). On each appointment, medical history will be updated and oral examination will be performed.

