### **3- Radiographic outcome measures:**

The criteria used to determine a successful radiographic outcome of the indirect pulp capping treatment is: (1) absence of interradicular or periapical radiolucencies, (2) absence of increased PDL space, (3) absence of resorptive defects all determined by periapical and bitewing radiographs. Radiographic assessment will be made through bitewings and periapical radiographs the day of intervention followed by the 6 and 12 months recalls as part of regular assessment and to collect research data. Teeth that present with clinical or radiographic signs or symptoms of irreversible pulpitis or necrosis will be assessed by an endodontist for proper endodontic treatment. Patient may be subjected to additional x-rays following pulp capping therapy for proper diagnosis of complications from treatment.

Radiographic research data collection: As part of research data collection, attempt will be made to assess changes to the remaining dentin thickness between recall appointments. To obtain period-identical x-rays, a specific film holder (Super-bite; Kerr) Rinn XCP film holder will be used to take bitewings. Software program (Dexis) will be used to measure digitally the remaining dentin thickness in 5-8 areas. The values will be averaged for estimated thickness.

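### The intervention is the only scheduled x-ray visit with no planned pregnancy test; a test on arrival is a cheap, low-severity improvement

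*Combined protocol and SAP*

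**What the plan says.** All references are to the combined protocol and SAP.

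- **Eligibility.** The Exclusion criteria rule out women who are pregnant or who plan a pregnancy within the coming year.
- **Screening (Study schedule).** "Pregnancy test will be provided to childbearing women subjects at screening appointment to rule out pregnancy". A named over-the-counter stick is to be used, and x-rays form part of the screening assessment.
- **Intervention (Study schedule).** This is the appointment after screening. The checks listed before treatment are these: "medical history will be reviewed, vital signs will be taken, and standard procedures for caries removal and restoration will be done". On allocation and treatment: "Treatment protocols will be randomized and the subjects will be treated as follow". After the restoration, "a bitewing radiograph will be taken as a baseline post-treatment documentation of the restoration and remaining dentin thickness". No pregnancy test is mentioned.
- **Follow-up (Study schedule).** The 3-month visit is clinical only. For later visits: "Pregnancy test will also be provided to childbearing women subjects at 6 months follow up (where x-rays will be taken for research purposes", and likewise at 12 months. A woman found to be pregnant is taken out of the study at once.
- **Radiographic outcome measures.** "As part of research data collection, attempt will be made to assess changes to the remaining dentin thickness between recall appointments". Films are scheduled for "the day of intervention followed by the 6 and 12 months recalls as part of regular assessment and to collect research data". Further films are allowed if a complication needs diagnosis.
- **Visit summary (Study schedule).** Subjects attend "for a total of 5 times of approximately 1-2 hours each in a one year period", and medical history is updated at each visit.

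**The concern.** Pregnancy is an exclusion, and eligibility on this point is confirmed by test once, at screening. Treatment comes at a later appointment, and the text sets no maximum gap. A woman who conceives in that gap, or whose pregnancy was too early to detect at screening, could be randomized, treated irreversibly and x-rayed while ineligible.

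If the pregnancy comes to light later, she is removed. She is then a treated subject whose remaining outcomes are lost, when she could have been a screen failure who was never allocated.

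The plan tests at 6 and 12 months because research films are taken then. The intervention film serves as the baseline for a measurement that the plan calls research data, so the same reason can sensibly be extended to it.

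**Working it through.** The plan gives no figure to reproduce. There are two steps: a cross-tabulation of the schedule, and a rough sizing of what an added test could find.

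**Step 1. Visits by x-ray and pregnancy test** (Study schedule; Radiographic outcome measures)

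| Scheduled visit | X-ray | Pregnancy test |
|---|---|---|
| Screening | yes | yes |
| Intervention | yes | none listed |
| 3 months | no | no |
| 6 months | yes | yes |
| 12 months | yes | yes |

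X-ray visits: 4 of 5. X-ray visits with a test: 3 of 4. The exception is the intervention. The schedule does not tie the preoperative periapical and bitewing films firmly to one appointment, but the table is the same whether they fall at screening or at the intervention.

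**Step 2. What an added test could detect**

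Assumptions, none of them in the documents:
- d = days from screening to intervention, taken as 0 to 56
- 6 months = 182 days
- a constant conception rate
- the same stick and the same detection lag at each test
- no woman reports a pregnancy herself

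Pregnancies first found at the 6-month test then arise from d + 182 days of conceptions. A test on the intervention day would have found those from d of these days. The share is d/(d + 182):

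- d near 0: about 0%
- d = 7: 7/189 = 3.7%
- d = 14: 14/196 = 7.1%
- d = 28: 28/210 = 13.3%
- d = 56: 56/238 = 23.5%

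The documents' only hint about d is the visit summary. All five visits fall within one year and the last is 12 months after the procedure. Read literally, 12 months − 12 months leaves d near 0.

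These shares are upper bounds for their scenario. A woman who conceived before the intervention has had longer to learn of it by the 3-month history update than one who conceived later. Allowing for self-report therefore lowers the share.

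An absolute number of women cannot be derived: the plan gives 150 teeth, but neither the number of subjects nor the number of women of childbearing potential.

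**The case against.** The existing schedule can be defended. The intervention is the next appointment after a visit at which a test has just been done, while the later tests come months on. Retesting after months but not at the very next visit is coherent. Women planning a pregnancy are already excluded, and history is reviewed at the intervention. On the literal timing the gain is about nil, and every larger figure rests on an assumed gap. Much of this stands, and it is why the point is low in severity.

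It does not remove the point. No maximum gap is stated. History cannot reveal a pregnancy that the woman does not know of, and the plan does not treat history as enough elsewhere: it updates history at 6 and 12 months and still tests.

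A reader might infer three stronger things that the documents do not support:

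- **That the plan breaks its own rule on research x-rays.** The rule is stated only for 6 and 12 months. The intervention film is described as documentation, and the Radiographic outcome measures section gives the films a mixed purpose, routine and research. Extending the reason is a reasonable inference and no more.
- **That the intervention is the only occasion for x-rays without a test.** Unscheduled diagnostic films are also allowed with no test mentioned, so the statement holds for scheduled visits only.
- **That fetal harm, or a material loss of data, has been shown.** The documents state no fetal risk from the materials or the films. A woman who tests positive on arrival contributes no outcomes either, so the gain is only that she is not randomized, treated and filmed while ineligible.

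The attachments were not available, and a test described only there cannot be ruled out.

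**Conclusion.** The point holds for scheduled visits and for the supplied text. The intervention is the one x-ray visit of four with no planned pregnancy test, and it is also where the randomized treatment is given and the dentin-thickness baseline is recorded.

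It is a small gap in confirming eligibility and protecting participants. Few women are likely to be affected. The share of 6-month detections that an added test could bring forward is near zero if the visits are close together. It reaches 3.7% to 23.5% only for assumed gaps of 7 to 56 days with no self-report. Most removals at 6 months would remain, since conceptions after treatment are untouched.

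Nothing follows for the sample size or for the Fisher's test in the Statistical Analysis Plan. This is a low-severity, cheap improvement.

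**What to change.** 1. In the Study schedule, under the clinical intervention, add the stick test already specified for screening. Give it to women of childbearing potential on arrival, before allocation, treatment and any film. Add the intervention to the list of tested visits in the follow-up text.
2. In Subject management and recruitment process, state that allocation is made only after this negative result. As written, allocation may follow screening approval, while the intervention text mentions randomization at the treatment stage, so the timing is open. With the order fixed, a positive test is a pre-randomization screen failure and not a post-randomization exclusion.
3. If an attachment already requires this test, say so in the main schedule.

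Cost: one more stick and a few minutes per woman of childbearing potential, a short amendment, and an occasional treatment appointment lost when a test is positive. The test will still miss pregnancies too recent to detect that day.

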## **Study Protocol**

**Study design:** Prospective, randomized, controlled, double-blinded study with three treatment arms.

**Sample size:** 150 teeth with deep caries of subjects willing and able to return to UIC COD for recall purposes.

**Eligibility criteria:** Subject must meet the inclusion criteria to participate in the study.

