## **Subject management and recruitment process**

Recruitment flyers (attachment #1) will be posted in different locations at the University of Illinois at Chicago campus.

Recruitment e-mails and messages will be sent to all the faculty and students attending predoctoral and postdoctoral clinics at UIC College of Dentistry. We will also send recruitment messages to all faculty, staff and students at the University of Illinois at Chicago using campus wide massmail listservs. In addition, medical records will be reviewed to determine subject eligibility.

Those subjects who will volunteer to participate will be asked to contact via phone the principle investigator or study coordinator, to comply with the inform consent process (attachment #3 – phone call script).

Once patients have been properly screened and approved for the study, the selection of the treatment that they will receive will be carried out randomly, using random integer generator ([www.random.org/integers/](http://www.random.org/integers/)). Teeth of subjects will be first stratified into those needing indirect pulp capping and direct pulp capping. Based on stratification, subjects will be randomized to one of three arms (indirect pulp capping) or one of two arms (direct pulp capping). Patients will be blinded to the treatment.

Subjects will be compensated in cash for their participation in the study.

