### **Data handling and Interpretation**

Data entry and database management will be done in an ongoing manner by project staff. All data will be entered in a timely manner once collected. The database will be password protected and housed in a secure location. The database will be backed up on a regular schedule with backup copies stored in a separate location from the primary file server. Quality of data entry will be enhanced by double entry data forms with field and range validation. Project management tools include graphical interfaces for tracking timeliness of data entry, missing data, graphical reports of actual recruitment versus recruitment goals on a real-time basis (i.e., updated as each participant is entered into the system), and other reports. The goal is 100% data accuracy.

Data and/or information which identifies the subject and the signed consent form may be looked at and/or copied for evaluation of the research protocol by: UIC Office for the Protection of Research Subjects, State of Illinois Auditors, State of Illinois Auditors and the research sponsor (Bisco Dental Products).

**Statistical Analysis Plan:** Descriptive data and rates of success will be calculated independently for indirect and direct therapies. Statistical analyses of proportions will be done using Fisher's test and 95% confidence intervals (CI).

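### After week one no step learns the tooth status of a subject who stops attending recalls, and root treatment or extraction is not named as failure; a record check and one call would recover part of it

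*Combined protocol and SAP*

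**What the plan says.** The Study schedule section places later data collection at the clinic visits: "The 3, 6 and 12 months appointments will be follow up appointments for data collection". Vitality and pain are assessed at each of these visits, and films at two of them: "At 6 and 12 months, periapical and bitewing radiographic evaluation will be performed for research purposes". The VAS section also puts the 3-, 6- and 12-month pain scores at the follow-up visits.

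Remote contact is limited to calls made "24 hours and one week after the intervention to remind them to complete the pain assessment form". Records are mentioned under Subject management and recruitment process, where "medical records will be reviewed to determine subject eligibility"; no use of them for outcomes is stated.

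Under Radiographic outcome measures, success of indirect capping is defined by "1) absence of interradicular or periapical radiolucencies, (2) absence of increased PDL space, (3) absence of resorptive defects". Root treatment and extraction are not named as failures. The same section sends teeth with signs or symptoms of irreversible pulpitis or necrosis to an endodontist and allows extra films to diagnose complications.

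The Statistical Analysis Plan paragraph says: "Descriptive data and rates of success will be calculated independently for indirect and direct therapies". It adds Fisher's test and 95% confidence intervals, and names no denominator, analysis set or rule for a missing outcome.

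**The concern.** A subject whose tooth became painful and was root-treated or extracted elsewhere may have less reason to come back for a research recall. If that subject never returns, nothing in the plan finds out what happened to the tooth, although that fact needs neither a visit nor a film. Loss of this kind depends on the outcome, so a rate computed on attenders would overstate success.

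Arms are small, so few failures are expected. In an assumed arm of 50 teeth, 10% failure is 5 teeth and 20% is 10 teeth. If 40% of failures are not seen, 2 and 4 of them go unrecorded.

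The failure definition is a second gap. An extracted tooth yields no film to judge, and a root-treated tooth could meet all three film criteria. Even when such an event is known, the plan does not say how to count it.

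**Working it through.** **Inputs from the documents.** 150 teeth (Study Protocol); three arms for indirect and two for direct capping (Subject management and recruitment process); recalls at 3, 6 and 12 months, with films at 6 and 12 (Study schedule). The 150 cannot be reproduced, because no alpha, power, effect size, expected rates or dropout allowance is given. It is neither confirmed nor disputed here.

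**Assumptions (none are in the documents).** True failure f = 10% and 20% in two arms; share of successes lost Ls = 15%; share of failures lost Lf = 40% (or 50%); share of lost status recovered = 60%; failures detectable by call or chart.

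1. *Attenders only.* Observed failure = f(1−Lf) / [f(1−Lf) + (1−f)(1−Ls)].
   - f = 10%: 0.060 / (0.060 + 0.765) = 7.3%; missing 1 − 0.825 = 17.5%.
   - f = 20%: 0.120 / (0.120 + 0.680) = 15.0%; missing 20%.
   - The difference is 7.7 points instead of 10. With Lf = 50% the rates are 0.050/0.815 = 6.1% and 0.100/0.780 = 12.8%, a difference of 6.7 points.

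2. *Range of the bias.* The excess in an attender-only success rate is d × (s_att − s_non), where d is the share lost and s_att and s_non are success among attenders and non-attenders. With s_att = 90% and s_non = 90%, 70% or 50%, it is 0, 2 or 4 points at d = 10%; 0, 4 or 8 at 20%; and 0, 6 or 12 at 30%. It is zero when loss is unrelated to outcome.

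3. *Effect on the arm difference.* Step 1 shrinks the difference because both arms share one loss pattern. With unequal loss the pattern changes. Let attenders in both arms succeed at 90%. One arm loses 10% of teeth, with 90% success among them, so all teeth give 90%. The other loses 20%, with 50% success among them, so 0.8 × 90% + 0.2 × 50% = 82%. The observed difference is 0 and the difference over all teeth is 8 points.

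4. *Recovery counted for both outcomes.* Multiply Lf and Ls by 0.4, giving 16% and 6%.
   - f = 10%: 0.084 / (0.084 + 0.846) = 9.0%; unknown 7%.
   - f = 20%: 0.168 / (0.168 + 0.752) = 18.3%; unknown 8%.
   - The difference is 9.2 points. With Lf = 50% the rates are 0.080/0.926 = 8.6% and 0.160/0.912 = 17.5%, a difference of 8.9 points.

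5. *Recovery counted for failures alone.* The rates become 0.084 / (0.084 + 0.765) = 9.9% and 0.168 / (0.168 + 0.680) = 19.8%. These look close to the truth, but only because of the assumed loss pattern. If 15% is lost whatever the outcome, attenders already give 10% and 20%. Adding 60% of lost failures alone gives 0.094/0.859 = 10.9% and 0.188/0.868 = 21.7%, which inflates failure in both arms. Counting recovered retained teeth as well gives 0.094/0.940 = 10% and 0.188/0.940 = 20%.

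6. *Bounds.* The width of best/worst-case bounds on a rate equals the share unknown. For tooth status it falls from 17.5–20 points to 7–8. For the radiographic rate a retained tooth without a film stays unknown, so the share falls only to 0.175 − 0.6 × 0.04 = 15.1% and 0.200 − 0.6 × 0.08 = 15.2%. In teeth: in an assumed arm of 50 with 10 unseen and 36 of 40 successful, success lies between 36/50 = 72% and 46/50 = 92%. Learning the tooth status of 5 of the 10 halves the width of the tooth-status bounds to 10 points.

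**The case against.** A reader might infer that outcomes come solely from the recalls and that every tooth treated elsewhere disappears from the success rates. The documents do not support that. The analysis plan states no denominator, so analysis of attenders only is an inference. Each appointment includes a history update and an oral examination, so outside treatment would come to light at any later recall the subject attends. Complications that present to the clinic go to an endodontist, with extra films if needed. The gap therefore concerns subjects who stop attending for good. A reader might also infer that the arm difference must be diluted; step 3 shows that this depends on assuming the same loss pattern in both arms.

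Other points on that side:

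- Entry is limited to "150 teeth with deep caries of subjects willing and able to return to UIC COD for recall purposes", subjects are paid, and missing data are tracked. These may reduce loss or reveal it, but they do not supply a lost tooth's status.
- A College record mainly shows College care. This stands, and is why a call is needed as well.
- A call cannot find a silent radiographic failure. This stands: the 60% recovery is optimistic to the extent that failures are visible only on film.
- The attachments and phone scripts are not in the text and may ask more. This cannot be checked, but the protocol states the timing and purpose of the calls.
- Without a failure definition and a missing-outcome rule, recovered status has no place in the analysis. This stands, and the fix covers both.

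**Conclusion.** The concern holds in a limited form. After week one, apart from complications that present to the clinic, planned outcome collection depends on attendance. No step learns the tooth status of a subject who stops attending, and the written criteria do not name root treatment or extraction as failure.

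If failure makes return less likely, success rates based on attenders are too high. By how much, and what this does to the arm difference, cannot be taken from the documents. The illustration (7.3% versus 15.0% against a true 10% versus 20%, improving to 9.0% versus 18.3%) shows what moderate outcome-related loss could do and what symmetric recovery could regain. It describes a tooth-status rate and rests wholly on the assumed rates. The bounds on the radiographic rate gain much less, from 17.5–20 points to about 15. Status not sought during the trial may be hard to obtain later, so this is worth changing.

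**What to change.** 1. *Study schedule.* For every subject who misses the 6- or 12-month recall and has not refused contact, the existing coordinator checks the College record and makes one scripted call or REDCap message. It asks whether the study tooth is retained, root-treated or extracted, with date and reason. A spoken pain score should not replace the drawn VAS.
2. *Radiographic outcome measures and Statistical Analysis Plan.* Count root treatment or extraction for pulpal or periapical reasons as failure, wherever it was done, and say how extractions for other reasons are shown.
3. *Statistical Analysis Plan.* Report a tooth-status rate by arm and stratum over all teeth with known status, counting recovered failures and recovered retained teeth alike, beside the radiographic success rate. Do not add recovered failures alone to the radiographic rate.
4. *Statistical Analysis Plan.* Report the number missing per arm and best/worst-case bounds over all randomized teeth.

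The cost is a few coordinator hours and changes to the script and possibly the consent wording; the coordinator, phone contact, REDCap and record review already exist in the plan. The downside is that recovered status is self- or chart-reported and less detailed than a film.
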